## ALGORITHM FOR PRIOR / CONCOMITANT:

### ORAL LURASIDONE TABLET PERIOD

START DATE	STOP DATE	ACTION
Known	Known	If stop date $<$ oral tablet start date, assign as prior  If both start date and stop date $\geq$ oral tablet start date, assign as concomitant  If stop date $\geq$ oral tablet start date and start date $<$ oral tablet start date, assign as both prior and concomitant
	Partial	Impute stop date as latest possible date (i.e. last day of month if day unknown or 31 st December if day and month are unknown), then:  If stop date $<$ oral tablet start date, assign as prior  If both start date and stop date $\geq$ oral tablet start date, assign as concomitant  If stop date $\geq$ oral tablet start date and start date $<$ oral tablet start date, assign as both prior and concomitant
	Missing	If stop date is missing then

Document:

Author:

Version Number:  
 Version Date:

Final Draft  
 11APR2019

Template No: CS\_TP\_BS016 Revision 4  
 Effective Date: 01Apr2016

Reference: CS\_WI\_BS005

START DATE	STOP DATE	ACTION
		
If start date <math>\geq</math> oral tablet start date, assign as concomitant
 
If start date <math><</math> oral tablet start date, assign as both prior and concomitant

Partial	Known	
Impute start date as earliest possible date (i.e. first day of month if day unknown or 1st January if day and month are unknown), then:
 
If stop date <math><</math> oral tablet start date, assign as prior
 
If both start date and stop date <math>\geq</math> oral tablet start date, assign as concomitant
 
If stop date <math>\geq</math> oral tablet start date and start date <math><</math> oral tablet start date, assign as both prior and concomitant

	Partial	
Impute start date as earliest possible date (i.e. first day of month if day unknown or 1st January if day and month are unknown)
 
Impute stop date as latest possible date (i.e. last day of month if day unknown or 31st December if day and month are unknown), then:
 
If stop date <math><</math> oral tablet start date, assign as prior
 
If both start date and stop date <math>\geq</math> oral tablet start date, assign as concomitant
 
If stop date <math>\geq</math> oral tablet start date and start date <math><</math> oral tablet start date, assign as both prior and concomitant

	Missing	
Impute start date as earliest possible date (i.e. first day of month if day unknown or 1st January if day and month are unknown), then:
 
If start date <math>\geq</math> oral tablet start date, assign as concomitant

Document:

Author:

Version Number:  
 Version Date:

Final Draft  
 11APR2019

Template No: CS\_TP\_BS016 Revision 4  
 Effective Date: 01Apr2016

Reference: CS\_WI\_BS005

Statistical Analysis Plan

PROTOCOL D1052024  
 Page 55 of 66

START DATE	STOP DATE	ACTION
		If start date < oral tablet start date, assign as both prior and concomitant
Missing	Known	If stop date < oral tablet start date, assign as prior  If stop date >= oral tablet start date, assign as both prior and concomitant
	Partial	Impute stop date as latest possible date (i.e. last day of month if day unknown or 31 st December if day and month are unknown), then:  If stop date < oral tablet start date, assign as prior  If stop date >= oral tablet start date, assign as both prior and concomitant
	Missing	Assign as both prior and concomitant

**DOUBLE-BLIND INJECTION PERIOD**

START DATE	STOP DATE	ACTION
Known	Known	If stop date >= injection date, assign as concomitant
	Partial	Impute stop date as latest possible date (i.e. last day of month if day unknown or 31 st December if day and month are unknown), then:  If stop date >= injection date, assign as concomitant
	Missing	If the subject is in ISAF population and start date <= end of study/early termination, assign as concomitant
Partial	Known	Impute start date as earliest possible date (i.e. first day of month if day unknown or 1 st January if day and month are unknown), then:

Document:

Author:

Version Number:  
 Version Date:

Final Draft  
 11APR2019

Template No: CS\_TP\_BS016 Revision 4  
 Effective Date: 01Apr2016

Reference: CS\_WI\_BS005

START DATE	STOP DATE	ACTION
		If stop date $\geq$ injection date, assign as concomitant
	Partial	Impute start date as earliest possible date (i.e. first day of month if day unknown or 1 st January if day and month are unknown)  Impute stop date as latest possible date (i.e. last day of month if day unknown or 31 st December if day and month are unknown), then:  If stop date $\geq$ injection date, assign as concomitant
	Missing	Impute start date as earliest possible date (i.e. first day of month if day unknown or 1 st January if day and month are unknown), then:  If start date $\leq$ end of study/early termination, assign as concomitant
Missing	Known	If stop date $\geq$ injection date, assign as concomitant
	Partial	If stop date $\geq$ injection date, assign as concomitant
	Missing	Assign as concomitant

## PRESENTATION OF VISITS

For outputs, visits will be represented as follows and in that order: Hours will be presented as appropriate based on the measurements.

Visit	Timepoint
Screening	Screening
Day -12	Day -12
Day -8	Day -8
Time Relative to Oral Lurasidone Dosing	
Day -7	Predose
	2 hours postdose
Day -6	Predose

Document:

Author:

Version Number:  
 Version Date:

Final Draft  
 11APR2019

Template No: CS\_TP\_BS016 Revision 4  
 Effective Date: 01Apr2016

Reference: CS\_WI\_BS005

Statistical Analysis Plan

PROTOCOL D1052024  
 Page 57 of 66

Visit	Timepoint
	2 hours postdose
Relative to Lurasidone or Placebo Injection Dosing	
Day 1	Day1 (Predose)
	2 hours postdose
	4 hours postdose
	6 hours postdose
	12 hours postdose
Baseline	Baseline
Day 2	24 hours post-injection dose
Day 3	48 hours post-injection dose
Day 4	72 hours post-injection dose
Day 5	96 hours post-injection dose
Day 6	120 hours post-injection dose
Day 7	144 hours post-injection dose
Day 15	336 hours post-injection dose
Day 22	504 hours post-injection dose
Day 29	672 hours post-injection dose
Day 61 (Follow-Up)	1440 hours post-injection dose

---

Document:

Author:

Version Number:  
 Version Date:

Final Draft  
 11APR2019

Template No: CS\_TP\_BS016 Revision 4  
 Effective Date: 01Apr2016

Reference: CS\_WI\_BS005

## LISTINGS

All listings will be ordered by the following:

- Cohort
- Dose Level
- Subject ID
- Date/time (where applicable) - listings of adverse events, concomitant medications, medical histories etc. should be sorted in chronological order, with earliest adverse event, medication or history coming first,

---

Document:

Author:

Version Number:  
Version Date:

Final Draft  
11APR2019

Template No: CS\_TP\_BS016 Revision 4  
Effective Date: 01Apr2016

Reference: CS\_WI\_BS005

## APPENDIX 3. PREDEFINED MARKEDLY ABNORMAL CRITERIA

### STANDARD ADULT MARKEDLY ABNORMAL POST-BASELINE LABORATORY VALUE (MAPLV) PARAMETERS – SI UNITS

Category		
Parameter Name	Low	High
Age/Gender Restriction, if any		
HEMATOLOGY		
WBC	$\leq 2.8 \times 10^9/\text{L}$	$\geq 16 \times 10^9/\text{L}$
Neutrophils (abs)	$< 0.5 \times 10^9/\text{L}$	$> 13.5 \times 10^9/\text{L}$
Lymphocytes (abs)	N/A	$> 12 \times 10^9/\text{L}$
Monocytes (abs)	N/A	$> 2.5 \times 10^9/\text{L}$
Eosinophils (abs)	N/A	$> 1.6 \times 10^9/\text{L}$
Basophils (abs)	N/A	$> 1.6 \times 10^9/\text{L}$
Neutrophils (relative)	$\leq 0.15$	$> 0.85$
Lymphocytes (relative)	N/A	$\geq 0.75$
Monocytes (relative)	N/A	$\geq 0.15$
Eosinophils (relative)	N/A	$\geq 0.10$
Basophils (relative)	N/A	$\geq 0.10$
Hemoglobin		
Male	$\leq 115 \text{ g/L}$	$\geq 190 \text{ g/L}$
Female	$\leq 95 \text{ g/L}$	$\geq 175 \text{ g/L}$
Hematocrit		
Male	$\leq 0.37$	$\geq 0.60$
Female	$\leq 0.32$	$\geq 0.54$
RBC	$\leq 3.5 \times 10^{12}/\text{L}$	$\geq 6.4 \times 10^{12}/\text{L}$
Platelet Count	$\leq 75 \times 10^9/\text{L}$	$\geq 700 \times 10^9/\text{L}$
SERUM CHEMISTRY		
Sodium	$< 130 \text{ mmol/L}$	$> 150 \text{ mmol/L}$
Potassium	$< 3 \text{ mmol/L}$	$> 5.5 \text{ mmol/L}$
Chloride	$\leq 90 \text{ mmol/L}$	$\geq 118 \text{ mmol/L}$
Calcium	$< 1.75 \text{ mmol/L}$	$\geq 3.1 \text{ mmol/L}$
Phosphate	$< 0.65 \text{ mmol/L}$	$> 1.65 \text{ mmol/L}$

Document:

Author:

Version Number:  
 Version Date:

Final Draft  
 11APR2019

Template No: CS\_TP\_BS016 Revision 4  
 Effective Date: 01Apr2016

Reference: CS\_WI\_BS005

Statistical Analysis Plan

PROTOCOL D1052024  
 Page 60 of 66

Category		
Parameter Name	Low	High
Age/Gender Restriction, if any		
AST (IU/L)	N/A	≥ 3 x ULN
ALT (IU/L)	N/A	≥ 3 x ULN
Alkaline Phosphatase (IU/L)	N/A	≥ 1.5 x ULN
Creatinine	N/A	≥ 177 umol/L
BUN	N/A	≥ 10.7 mmol/L
Total bilirubin (mg/dL)	N/A	≥ 34.2 umol/L OR > 2 x ULN
Total protein	≤ 45 g/L	≥ 100 g/L
Albumin	≤ 25 g/L	N/A
Total-Cholesterol (fasting)	N/A	> 7.76 mmol/L
HDL-Cholesterol (fasting)	< 0.78 mmol/L	N/A
LDL-Cholesterol (fasting)	N/A	> 4.14 mmol/L
Triglycerides	N/A	> 3.42 mmol/L
Uric acid		
Male	N/A	> 595 umol/L
Female	N/A	> 476 umol/L
Glucose (Fasting)	< 2.78 mmol/L	> 13.9 mmol/L
Prolactin	NA	Female: >= 146.0 ng/mL Male: >= 88.5 ng/mL
COAGULATION		
aPTT (sec)	N/A	> 1.5 ULN
INR (ratio)	N/A	> 1.5 ULN
THYROID FUNCTION		
Free T3	< 3.07 pmol/L	> 6.38 pmol/L
Free T4	< 9.65 pmol/L	> 22.5 pmol/L

---

Document:

Author:

Version Number:  
 Version Date:

Final Draft  
 11APR2019

Template No: CS\_TP\_BS016 Revision 4  
 Effective Date: 01Apr2016

Reference: CS\_WI\_BS005

---

## APPENDIX 4. LIST OF TABLES, FIGURES, AND LISTINGS

Number	Title
Table 14.1.1	Subject Disposition by Treatment - All Subjects
Table 14.1.2	Important Protocol Deviation (IPD) by Treatment - Injectable Safety Population
Table 14.1.3	Demographics and Baseline Characteristics by Treatment - Injectable Safety Population
Table 14.1.4.1	Medical History by Treatment - Injectable Safety Population
Table 14.1.4.2	Psychiatric History by Treatment - Injectable Safety Population
Table 14.1.5.1	Prior Medications by Treatment - Safety Population
Table 14.1.5.2	Concomitant Medications by Treatment - Safety Population
Table 14.2.1.1	Lurasidone Serum Concentrations (ng/mL) by Scheduled Timepoint and Dose Pharmacokinetic Population
Table 14.2.1.2	Metabolite Serum Concentrations (ng/mL) by Scheduled Time and Dose - Pharmacokinetic Population
Table 14.2.2.1	Lurasidone Serum Pharmacokinetic Parameters by Dose and Gender Following Lurasidone Injection - Pharmacokinetic Population
Table 14.2.2.2	Metabolite Serum Pharmacokinetic Parameters by Dose and Gender Following Lurasidone Injection - Pharmacokinetic Population
Table 14.2.3.1	Dose Proportionality Assessment - Lurasidone - Pharmacokinetic Population
Table 14.2.3.2	Dose Proportionality Assessment - Lurasidone Metabolites - Pharmacokinetic Population
Table 14.2.4.1	Lurasidone Urine Pharmacokinetic Parameters by Dose and Gender Following Lurasidone Injection - Pharmacokinetic Population
Table 14.2.4.2	Metabolite Urine Pharmacokinetic Parameters by Dose and Gender - Pharmacokinetic Population
Table 14.2.5	Positive and Negative Syndrome Scale (PANSS) Total Score: Actual and Change from Baseline by Scheduled Timepoint and Treatment - Pharmacodynamic Population
Table 14.3.1.1	Overall Summary of Adverse Events - Injectable Safety Population
Table 14.3.1.2	All Adverse Events by Treatment - Safety Population

---

Document:

Author:

Version Number:  
 Version Date:

Final Draft  
 11APR2019

Template No: CS\_TP\_BS016 Revision 4  
 Effective Date: 01Apr2016

Reference: CS\_WI\_BS005

Statistical Analysis Plan

PROTOCOL D1052024  
 Page 62 of 66

Number	Title
Table 14.3.1.3	All Adverse Events by Severity and Treatment - Safety Population
Table 14.3.1.4	All Adverse Events by Relationship to Treatment - Safety Population
Table 14.3.1.5	Duration of All Injection Site Reaction Related AEs in Days by Treatment - Injectable Safety Population
Table 14.3.2.1	All Serious Adverse Events by Treatment - Safety Population
Table 14.3.2.2	Adverse Events Leading to Study Discontinuation - Injectable Safety Population
Table 14.3.4.1.1	Serum Chemistry: Actual Value and Change from Baseline by Scheduled Timepoint and Treatment - Injectable Safety Population
Table 14.3.4.1.2	Serum Chemistry: Shift from Baseline by Scheduled Timepoint and Treatment - Injectable Safety Population
Table 14.3.4.2.1	Hematology Parameters: Actual Value and Change from Baseline by Scheduled Timepoint and Treatment - Injectable Safety Population
Table 14.3.4.2.2	Hematology: Shift from Baseline by Scheduled Timepoint and Treatment – Injectable Safety Population
Table 14.3.4.3.1	Urinalysis: Actual Value and Change from Baseline by Scheduled Timepoint and Treatment - Injectable Safety Population
Table 14.3.4.3.2	Urinalysis: Shift from Baseline by Scheduled Timepoint and Treatment - Injectable Safety Population
Table 14.3.4.4	Summary of Markedly Abnormal Post-Baseline Laboratory Value (MAPLV) by Treatment - Injectable Safety Population
Table 14.3.5.1	Vital Signs: Actual Value and Change from Baseline by Scheduled Timepoint and Treatment - Injectable Safety Population
Table 14.3.5.2	Summary of Abnormal Post-Baseline Vital Signs (MAPVS) Values by Treatment - Injectable Safety Population
Table 14.3.5.3	Incidence of Orthostatic Hypotension and Orthostatic Tachycardia by Treatment - Injectable Safety Population
Table 14.3.5.4.1	ECG: Actual Value and Change from Baseline by Scheduled Timepoint and Treatment - Injectable Safety Population
Table 14.3.5.4.2	Summary of ECG Categories of Markedly Abnormal Criteria by Treatment - Injectable Safety Population

Document:

Author:

Version Number:  
 Version Date:

Final Draft  
 11APR2019

Template No: CS\_TP\_BS016 Revision 4  
 Effective Date: 01Apr2016

Reference: CS\_WI\_BS005

Statistical Analysis Plan

PROTOCOL D1052024  
 Page 63 of 66

Number	Title
Table 14.3.5.5.1	Summary of Columbia Suicide Severity Rating Scale (CSSRS) by Scheduled Timepoint and Overall Screening/Baseline and Last Visit Questionnaire - Injectable Safety Population
Table 14.3.5.6.1	Investigator Injection Site Reaction by Treatment and Schedule Timepoint - Injectable Safety Population
Table 14.3.5.6.2	Subject Injection Site Reaction Pain by Treatment and Schedule Timepoint - Injectable Safety Population
Figure 14.2.1.1	Mean (+SD) Lurasidone Serum Concentration-time Profiles by Dose on Linear and Semi-logarithmic Scales - Pharmacokinetic Population
Figure 14.2.1.2	Mean (+SD) ID-14283 Serum Concentration-time Profiles by Dose on Linear and Semi-logarithmic Scales - Pharmacokinetic Population
Figure 14.2.1.3	Mean (+SD) ID-14326 Serum Concentration-time Profiles by Dose on Linear and Semi-logarithmic Scales - Pharmacokinetic Population
Figure 14.2.1.4	Mean (+SD) ID-11614 Serum Concentration-time Profiles by Dose on Linear and Semi-logarithmic Scales - Pharmacokinetic Population
Figure 14.2.1.5	Mean (+SD) ID-20219 Serum Concentration-time Profiles by Dose on Linear and Semi-logarithmic Scales - Pharmacokinetic Population
Figure 14.2.1.6	Mean (+SD) ID-20220 Serum Concentration-time Profiles by Dose on Linear and Semi-logarithmic Scales - Pharmacokinetic Population
Figure 14.2.2.1	Individual Lurasidone Serum Concentration-time Profiles by Dose on Linear and Semi-logarithmic Scales - Safety Population
Figure 14.2.2.2	Individual ID-14283 Serum Concentration-time Profiles by Dose on Linear and Semi-logarithmic Scales - Injectable Safety Population
Figure 14.2.2.3	Individual ID-14326 Serum Concentration-time Profiles by Dose on Linear and Semi-logarithmic Scales - Injectable Safety Population
Figure 14.2.2.4	Individual ID-11614 Serum Concentration-time Profiles by Dose on Linear and Semi-logarithmic Scales - Injectable Safety Population
Figure 14.2.2.5	Individual ID-20219 Serum Concentration-time Profiles by Dose on Linear and Semi-logarithmic Scales - Injectable Safety Population

Document:

Author:

Version Number:  
 Version Date:

Final Draft  
 11APR2019

Template No: CS\_TP\_BS016 Revision 4  
 Effective Date: 01Apr2016

Reference: CS\_WI\_BS005

Statistical Analysis Plan

PROTOCOL D1052024  
 Page 64 of 66

Number	Title
Figure 14.2.2.6	Individual ID-20220 Serum Concentration-time Profiles by Dose on Linear and Semi-logarithmic Scales - Injectable Safety Population
Figure 14.2.3	Individual, Median, and Geometric Mean Lurasidone Serum Pharmacokinetic Parameters versus Dose - Pharmacokinetic Population
Figure 14.2.4	Individual, Median, and Geometric Mean ID-14283 Serum Pharmacokinetic Parameters versus Dose - Pharmacokinetic Population
Figure 14.2.5	Individual, Median, and Geometric Mean ID-14326 Serum Pharmacokinetic Parameters versus Dose - Pharmacokinetic Population
Figure 14.2.6	Individual, Median, and Geometric Mean ID-11614 Serum Pharmacokinetic Parameters versus Dose - Pharmacokinetic Population
Figure 14.2.7	Individual, Median, and Geometric Mean ID-20219 Serum Pharmacokinetic Parameters versus Dose - Pharmacokinetic Population
Figure 14.2.8	Individual, Median, and Geometric Mean ID-20220 Serum Pharmacokinetic Parameters versus Dose - Pharmacokinetic Population
Figure 14.2.9.1	Mean Urine Lurasidone Cumulative Ae versus Time by Dose - Pharmacokinetic Population
Figure 14.2.9.2	Mean Urine ID-14283 Cumulative Ae versus Time by Dose - Pharmacokinetic Population
Figure 14.2.9.3	Mean Urine ID-14326 Cumulative Ae versus Time by Dose - Pharmacokinetic Population
Figure 14.2.9.4	Mean Urine ID-11614 Cumulative Ae versus Time by Dose - Pharmacokinetic Population
Figure 14.3.1	Incidence of any post-injection Adverse Events by Study Day - Injectable Safety Population
Listing 16.2.1.1	Listing of Subject Disposition - All Screened Subjects
Listing 16.2.1.2	Listing of Screen Failure Subjects
Listing 16.2.2.1	Listing of Important Protocol Deviations - Injectable Safety Population
Listing 16.2.2.2	Listing of Study Eligibility and Continuation Criteria
Listing 16.2.4.1	Listing of Demographics and Baseline Characteristics - Oral Safety Population
Listing 16.2.4.2	Listing of Medical History - Oral Safety Population
Listing 16.2.4.3	Listing Psychiatric History - Oral Safety Population

Document:

Author:

Version Number:  
 Version Date:

Final Draft  
 11APR2019

Template No: CS\_TP\_BS016 Revision 4  
 Effective Date: 01Apr2016

Reference: CS\_WI\_BS005

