### **3.3. STUDY ENDPOINTS**

#### **3.3.1. SAFETY ENDPOINTS**

Incidence of AEs, serious adverse events (SAEs), and AEs leading to study discontinuation

Incidence of injection site-related reactions, including injection site pain, injection site erythema, injection site induration, injection site ulcer, injection site granuloma and injection site swelling

Observed values and changes from baseline in clinical laboratory tests (hematology, serum chemistry, urinalysis, coagulation, and liver function), vital signs (respiratory rate, body temperature, supine blood pressure, and pulse), orthostatic effects (based on blood pressure and pulse rate), and 12-lead electrocardiograms (ECGs) parameters

Incidence and severity of subjects with suicidal ideation or suicidal behavior using the Columbia Suicide Severity Rating Scale (C-SSRS)

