## 6.1. SAFETY [SAF] POPULATIONS

### 6.1.1. ORAL LURASIDONE SAFETY [OSAF] POPULATION

The Oral Lurasidone safety population (OSAF) will contain all subjects who signed the study specific informed consent and received at least one dose of Lurasidone oral tablet.

This population will be used for analysis of concomitant medications and adverse events data along with ISAF population.

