### 6.1.2. INJECTABLE SAFETY [ISAF] POPULATION

The Injectable safety population (ISAF) will contain all subjects in the RND set who received injection of the double-blind study drug. Subjects will be classified according to treatment received.

This population will be used for analysis of baseline and safety data.

For summary tables in which data from both ISAF and OSAF populations are summarized, the term Safety Population will be used.

---

Document:

Author:

Version Number:  
Version Date:

Final Draft  
11APR2019

Template No: CS\_TP\_BS016 Revision 4  
Effective Date: 01Apr2016

Reference: CS\_WI\_BS005

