### **18. SAFETY OUTCOMES**

Adverse events and concomitant meds summary tables will be presented by oral and injectable treatment groups in the safety population. Injection site reaction related AEs will be presented by ISAF. All other safety summary data will be presented using ISAF population. OSAF population will be used for listings. There will be no statistical comparisons between the treatment groups for safety data, unless otherwise specified with the relevant section. Summary tables will be presented by treatment (dose level of Lurasidone injectable suspension and pooled placebo).

AEs and all other safety data will be listed and summarized descriptively by treatment group (dose level of Lurasidone injectable suspension and pooled placebo) in tabular or graphical formats, as appropriate. Observed values, as well as change from baseline for clinical safety laboratories, vital signs, and ECGs will be listed and summarized descriptively in tabular formats, as appropriate. Any clinically significant results in clinical safety laboratories, vital signs, and ECGs will be listed and summarized. Frequency and severity of suicidality, based on the C-SSRS, will be listed and summarized.

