#### **18.1.2. AEs LEADING TO DISCONTINUATION OF STUDY**

AEs leading to discontinuation of the study will be identified by using the AE page of the electronic case report form (eCRF), where “Caused Study Discontinuation” is answered as “Yes”.

Summary and Listing of AEs leading to discontinuation of the study, will be presented.

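### SAP Appendix 4 puts the overall AE summary and the table of AEs leading to discontinuation on injected subjects only, against the SAP's own rule in section 18

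*SAP*

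**What the plan says.** The SAP defines two safety populations. The oral one (OSAF, section 6.1.1) holds consented subjects who "received at least one dose of Lurasidone oral tablet", and the SAP adds: "This population will be used for analysis of concomitant medications and adverse events data along with ISAF population". The injectable one (ISAF, section 6.1.2) "will contain all subjects in the RND set who received injection of the double-blind study drug". Where a table draws on both, section 6.1.2 calls the result the Safety Population.

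Section 18 sets the rule for AE tables: "Adverse events and concomitant meds summary tables will be presented by oral and injectable treatment groups in the safety population". The only AE exception it makes is for injection-site-reaction AEs, which go on ISAF. Section 18.1.1 repeats that AE tables cover both the oral and the injection period. Section 18.1.2 names no population: "Summary and Listing of AEs leading to discontinuation of the study, will be presented".

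The safety endpoints in section 3.3.1 include "Incidence of AEs, serious adverse events (SAEs), and AEs leading to study discontinuation".

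In Appendix 4, Table 14.3.1.1 is "Overall Summary of Adverse Events - Injectable Safety Population" and Table 14.3.2.2 is "Adverse Events Leading to Study Discontinuation - Injectable Safety Population".

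**The concern.** The run-in serves to identify subjects who do not tolerate lurasidone. Protocol section 6.1 allows randomization only after two 80 mg oral doses and five days of monitoring without moderate AEs. AEs are collected from the first tablet (SAP section 18.1). A subject who stops at this stage because of an AE belongs to OSAF but never to ISAF, so both summaries miss that subject by construction.

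At stake is whether the AE outputs agree with one another. A reader who compares Table 14.3.2.2 with its listing, or the overall summary with the detailed AE tables, could find different subjects and have no explanation in the SAP. Table 14.3.2.2 is also the only dedicated summary of AEs leading to discontinuation, so oral-period stops would have no tabulated incidence.

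**Working it through.** **Step 1: titles against the rule.** The AE outputs in Appendix 4 and their populations are:

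| Output | Content | Population in title | Follows section 18? |
|---|---|---|---|
| Table 14.3.1.1 | Overall AE summary | Injectable | No |
| Table 14.3.1.2 | All AEs | Safety | Yes |
| Table 14.3.1.3 | AEs by severity | Safety | Yes |
| Table 14.3.1.4 | AEs by relationship | Safety | Yes |
| Table 14.3.1.5 | Duration of injection-site AEs | Injectable | Yes (stated exception) |
| Table 14.3.2.1 | SAEs | Safety | Yes |
| Table 14.3.2.2 | AEs leading to discontinuation | Injectable | No |
| Listing 16.2.7.3 | AEs leading to early discontinuation | Oral safety | Listings use OSAF |

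The two tables marked No are not about injection-site reactions, so the exception does not cover them.

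**Step 2: one subject traced through.** Take a subject who has a serious AE after the Day -7 tablet and leaves the study on Day -5. The subject is in OSAF and not in ISAF. The event appears in Tables 14.3.1.2 to 14.3.1.4, in SAE Table 14.3.2.1 and in Listing 16.2.7.3. It does not appear in Table 14.3.1.1, nor in Table 14.3.2.2, which directly follows the SAE table. Disposition (Table 14.1.1, all subjects) would show the exit and its reason, but not the event by system organ class and preferred term.

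**Step 3: planned numbers.** The SAP's figure for injected subjects reproduces: 5 cohorts x 8 = 40 (30 active, 10 placebo). SAP section 4.4 plans about 70 overall, so 70 - 40 = 30 are planned but not injected, which is 30/70 = 42.9%. The documents do not say how many of these 30 would take a tablet, or how many would stop for an AE.

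**Step 4: what the oral column would show.** Let m be the number who stop before injection because of an oral-period AE. This is an assumption, and its range is 0 to 30. If all 40 injections are given and nobody else takes oral drug without being injected, the oral column shows m/(40 + m). Orally dosed alternates would enlarge the denominator and lower the percentage. Table 14.3.2.2 as titled counts none of the m.

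| m (assumed) | From this source, as titled | Oral column after the change |
|---|---|---|
| 0 | 0/40 | 0/40 = 0.0% |
| 1 | 0/40 | 1/41 = 2.4% |
| 5 | 0/40 | 5/45 = 11.1% |
| 10 | 0/40 | 10/50 = 20.0% |
| 30 | 0/40 | 30/70 = 42.9% |

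The last row is an extreme bound, not an expectation.

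**The case against.** A reader might infer that a stated safety endpoint drops everyone who stops because of run-in AEs. The documents do not support that, for four reasons.

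- The protocol's Safety population (section 14.2) is limited to randomized and dosed subjects, and the safety objective concerns a single dose of the injectable. Protocol Table 4 classes an enrolled but non-randomized subject as a randomization failure and reserves early termination for randomized subjects. SAP section 4.7 declares no change from the protocol. The protocol therefore does not clearly require oral-only subjects in this endpoint.
- These subjects are reported elsewhere: in the OSAF listing, the Safety-population AE and SAE tables, and disposition.
- Not everyone is excluded. A subject with an oral-period AE who is injected and later withdraws because of it is in ISAF.
- The evidence is titles only. The templates are supplied separately (SAP section 8), and Appendix 4 has other uneven titles: Figure 14.2.2.1 is on the Safety population while Figures 14.2.2.2 to 14.2.2.6 are on the injectable one.

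It is also open whether a subject who fails the oral tolerability check would have the eCRF study-discontinuation field in section 18.1.2 marked yes, although placing the listing on OSAF suggests that such records are expected.

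All of this limits the point without removing it. The SAP chose to add OSAF, assigned it to AE analysis and wrote a rule for AE tables. Two of its tables break that rule without a stated exception. A listing gives no incidence, and disposition does not give AE terms.

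**Conclusion.** The point holds as an internal contradiction. Section 18 puts AE summaries on the Safety population by oral and injectable group, and Appendix 4 puts Tables 14.3.1.1 and 14.3.2.2 on injected subjects. As titled, both leave out subjects who stop before injection because of an oral-period AE, so Table 14.3.2.2 would not match its listing or the SAE table beside it if any such subject occurs. Columns for the injection groups are unaffected.

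The size cannot be derived from the documents. It may be zero, and 30 is only a ceiling, because the 30 non-injected subjects may include screen failures and alternates discharged unused. The contradiction itself does not depend on the count. The conclusion assumes that the shells follow their titles in Appendix 4.

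**What to change.** Move Tables 14.3.1.1 and 14.3.2.2 to the Safety population. Add the Oral Lurasidone 80 mg column already defined in SAP Appendix 1, with OSAF as its denominator, beside the injection groups and pooled placebo. Leave the injection-group columns unchanged. Name the population in section 18.1.2 so that text and title agree.

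If the sponsor does want these two summaries limited to injected subjects, sections 18 and 18.1.2 should state that exception and say that oral-period stops are listed only. That would remove the contradiction but leave those stops without a tabulated incidence, so the first option is preferable.

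The cost is two table shells and a sentence of text. The data are already collected and already feed the OSAF listing.
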